10.4 DESCRIPTION OF STATISTICAL METHODS

10.4.1 GENERAL APPROACH

Categorical data descriptive statistics will be presented as percentages, while continuous data descriptive statistics will be presented with the mean and standard deviation. Due to our goal of establishing estimates of centrality and spread for various measures to be used in future studies, no inferential tests will take place in this study.

Version 01.2 Protocol:201607761 Version 20.2 Version 01.2

10.4.2 ANALYSIS OF THE PRIMARY ENDPOINT(S)

Enrollment rate:

This will be assessed every 3 months until the end of the enrollment period. It will be reported as number of participants enrolled per 3 months. It will also be reported as percentage of all the patients screened.

Retention rate:

This will be assessed every 3 months. It will be reported as number of participants completed the study per protocol per 3 months. It will also be reported as percentage of all the patients screened.

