Secondary Obective:

To evaluate effect of fluoxetine on HCVR and peri-ictal respiratory

depression in drug resistant epilepsy patients.

Version 01.2 Protocol:201607761 Version 01.2

Endpoint Primary End point:

Study recruitment rate assessed every 3 months through the study

completion

Study retention rate assessed every 3 months through the study completion

Secondary End point:

Change in mood score using PHQ-9 score

Change in minute ventilation during HCVR testing

Change in slope of HCVR

Difference in duration of abnormal breathing in periocal period

Difference in oxygen saturation during periotal period

Difference in CO₂ level in periotal period

Exploratory End points: Change in VRTCO₂

Change in time to VRTCO₂

Change in time to end of HCVR testing

Population: Subjects age 18-75 years, both genders, drug resistant epilepsy with no

prior severe depression or other psychiatry co-morbidities but otherwise healthy, mostly living in State of Iowa will be screened for this study.

Phase: 2 Number of Sites 1

enrolling participants:

[figure not shown]
Description of Study Fluoxetine, given by mouth with a standard titration over 6 weeks.

Agent: 10 mg for 1 week, 20 mg for 1 week, 40 mg for 2 weeks, 20 mg for 1 week,

10 mg for 1 week then STOP

Study Duration: 2 years **Participant Duration:** 6 weeks

Version 01.2 Protocol:201607761 06/28/2017

Version 01.2 Protocol:201607761 06/28/2017

I KEY ROLES

[name]

Role: Principal investigator

Institution: The University of Iowa,

Address: [name]

[contact] Email: [contact]

[name] Role: Co-Investigator

Institution: The University of Iowa,

Address: [name]

[contact] Email: [contact]

[name] Role: Co-Investigator

Institution: The University of Iowa,

Address: [name]

[contact] Email: [contact]

[name] PhD

Role: Co-Investigator

Institution: The University of Iowa,

Address: [name]

[contact]

Email: [contact]

[name] [name] Role: Biostatistician

Institution: The University of Iowa,

Address: [name]

[contact] Email: [contact]

[name] PhD

Role: Independent Medical Examiner Institution: The University of Iowa,

Address: [name]

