3 OBJECTIVES AND PURPOSE

Primary Object: To assess feasibility of successfully enrolling subjects

Secondary Obect: To evaluate effect of fluoxetine on HCVR and peri-ictal respiratory depression in drug resistant epilepsy patients.

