4.2.1 PRIMARY ENDPOINT

Study recruitment rate assessed every 3 months Study completion rate assessed every 3 months

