5.2 PARTICIPANT EXCLUSION CRITERIA

- 1. Progressive neurological disease.
- 2. Clinical diagnosis of bipolar disease, panic disorder, psychosis or severe depression, or PHQ-9 score > 20
- 3. Patients with prior hospitalization related to depression or Electroconvulsive therapy.
- 4. History of suicidal ideation or intent in past or present
- 5. Clinical history or laboratory evidence of hepatic or renal insufficiency.
- 6. Pregnant or lactating women.
- 7. Current heavy alcohol use (>14 drinks per week for men or >7 drinks per week for women) or) known medical disorder related to alcohol use or current illicit drug use.
- 8. Patients with recent use (<1 month) or already taking fluoxetine or other selective serotonin reuptake inhibitors (SSRIs).
- 9. Concurrent use of monoamine oxidase inhibitors, antipsychotic agents, antidepressant agents other than SSRIs or frequent use of triptan agents (>2/week).
- 10. History of a previous allergic reaction or adverse effects with fluoxetine, hypersensitive reaction-anaphylaxis; laryngeal edema; hives
- 11. History of serotonin syndrome.
- 12. History of uncontrolled pulmonary or cardiac illness.
- 13. Patients with normal hypercapnic ventilatory response, i.e. HCVR slope of ≥ 2.0
- 14. Patients with known prolong QT interval
- 15. Patients with family history of prolong QT interval
- 16. Patients with family history of sudden cardiac death.

Version 01.2 Protocol:201607761 06/28/2017

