5.3 STRATEGIES FOR RECRUITMENT AND RETENTION

Patients, 18-75 year age, with epilepsy being treated at EMU & neurology clinic at the University of Iowa Hospital & Clinics will be screened for their eligibility for this study. Subjects with lack of consent capacity including severe mentally ill, prisoners, cognitive impaired, pregnant, children, prisoner, non English speaking and employee vounteers will be excluded from the study.

Approximately, 100 subjects will undergo HCVR testing for screening; Eligible subjects will be randomized to fluoxetine vs placebo, until each group has 20 completed subjects.

Anticipated accrual rate: 2/month

Number of sites and participants in US site: 1

Source of participants and Recruitment venues: Patients, 18-75 year age, with epilepsy being treated at EMU & neurology clinic at the University of Iowa Hospital & Clinics

Types of advertisements planned: Emails with information regarding the study will be distributed among neurology physicians working at the University of Iowa Hospitals & Clinics.

Subjects will be contacted via telephone as a part of study protocol followup which may improve retention.

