7.3 STUDY SCHEDULE

7.3.1 SCREENING

Potential subjects for the study will be are referred by treating neurologists at neurology clinic & EMU at the University of Iowa Hospitals & Clinics.

- Referred subjects are screened based on review of medical history & Iowa SSRI screening questionnaire.
- Written informed consent will be obtained from the participants
- Subjects will undergo HCVR testing for determining eligibility for enrolling in intervention part of the study

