10 STATISTICAL CONSIDERATIONS

10.1 STATISTICAL AND ANALYTICAL PLANS

This study is designed as a pilot to obtain estimates to be used in future studies. We will report the descriptive statistics for both treatment groups for each endpoint.

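### The primary retention rate is a percentage of all patients screened, so it mixes ineligibility with dropout; completers divided by randomised is never called for

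*Combined protocol and SAP*

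**What the plan says.** Section 10.4.2 gives two forms of the retention rate: a count per 3 months and a percentage. The numerator is those who finished per protocol, and the text runs "participants completed the study per protocol per 3 months. It will also be reported as percentage of all the patients screened". The enrolment rate in the same section has the same screened denominator.

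No other section supplies a different denominator:

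- The Protocol Summary lists "Study retention rate assessed every 3 months through the study" completion, and section 4.2.1 lists "Study completion rate assessed every 3 months". The labels differ and neither has a denominator.
- Sections 4.1 and 5.5 mention completion rates, also without one.
- Section 10.4.5 has retention in its title but describes only how adherence is assessed.

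Four other statements bear on the point:

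- Section 10.1 says the pilot is meant to supply estimates for later studies and adds: "We will report the descriptive statistics for both treatment groups for each endpoint".
- Section 5.2 excludes "Patients with normal hypercapnic ventilatory response, i.e. HCVR slope of" 2.0 or more, so the screening test itself decides eligibility.
- Section 5.3 expects that about "100 subjects will undergo HCVR testing for screening; Eligible subjects will be randomized to fluoxetine vs placebo, until each group has 20 completed subjects".
- Section 7.3.1 uses the word screened for an earlier step: "Referred subjects are screened based on review of medical history" and a questionnaire, before consent and HCVR testing.

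**The concern.** Retention normally means the share of randomised participants who stay to the end. The planned denominator also contains everyone who was screened and never randomised. Most of these will be patients whose HCVR slope was too high, which says nothing about dropout.

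A later trial needs dropout after randomisation to set its sample size. A reader who takes the planned percentage at its label would see about 40% in a study that kept every participant. Section 5.5 names poor recruitment or completion rates as grounds for stopping, and a blended figure cannot show which of the two is poor.

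The percentage also cannot be split by treatment group, because screened patients who are not randomised have no arm. Attrition by arm matters here. The analysis set is per protocol (section 10.3), observations with missing data are dropped (section 10.4.3), and after withdrawal only safety contact is attempted (section 5.4.2).

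**Working it through.** The plan states no retention figure, dropout rate or formal sample size (section 10.5), so there is no figure to reproduce. The check is whether the planned percentage measures retention.

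**Inputs**

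- HCVR-tested: about 100 (section 5.3).
- Randomised: 40 (Protocol Summary, Précis).
- Completers: 20 in each of two groups, so 40 (section 5.3).
- Dropout: assumed 0% to 20%.

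**Identity**, cumulatively or within one randomisation cohort:

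completers/screened = (randomised/screened) × (completers/randomised)

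The first factor is screening yield and the second is retention.

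**(a) 100 tested, 40 randomised**

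| Assumed dropout | Completers | Completers/randomised | Planned percentage (completers/screened) |
|---|---|---|---|
| 0% | 40 | 100% | 40% |
| 10% | 36 | 90% | 36% |
| 20% | 32 | 80% | 32% |

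The ceiling is the yield, 40/100 = 40%.

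**(b) 100 tested, recruitment continuing until 40 complete**, as section 5.3 can be read

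| Randomised | Yield | Retention | Planned percentage |
|---|---|---|---|
| 40 | 0.40 | 40/40 = 100% | 40% |
| 45 | 0.45 | 40/45 = 89% | 40% |
| 50 | 0.50 | 40/50 = 80% | 40% |

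Three different retention rates give the same reported figure.

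**The reverse case.** With retention fixed at 90%, the planned percentage is 0.9 × 0.3 = 27%, 0.9 × 0.4 = 36%, 0.9 × 0.5 = 45% or 0.9 × 0.6 = 54% when 30%, 40%, 50% or 60% of those screened are randomised. It moves with eligibility although dropout has not changed.

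**Recovery.** Dividing the two cumulative planned percentages gives overall retention: with 36 completers, 36%/40% = 90%. This requires that enrolled means randomised. It also fails within a single 3-month window, because follow-up runs from about 4 to 7 weeks (sections 7.3.3 and 7.3.4) and the completers in a window are partly not the people enrolled in it.

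**Precision of the proper ratio** (exact Clopper-Pearson 95% intervals): 36/40 = 90%, 76.3% to 97.2%; 18/20 = 90%, 68.3% to 98.8%.

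**The case against.** The strongest reply is that little is at stake. Completers per patient screened is a legitimate feasibility measure, since the primary objective is "To assess feasibility of successfully enrolling subjects". Section 10.4.2 states the denominator beside the figure, both counts are planned, and one division recovers overall retention. No hypothesis or success threshold depends on it. All of this stands, and it limits the consequence. It does not make the figure a retention rate, and a primary endpoint should not have to be reconstructed by its readers.

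Three narrower objections have some force:

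- Example (b) holds the number tested at 100 and lets yield rise in step with dropout. If yield stayed at 40%, randomising 50 would take 50/0.40 = 125 tested, and 40/125 = 32%, so the figure would move. Example (b) shows that the measure can fail to identify dropout; it is not a forecast.
- The sentence in section 10.1 about both treatment groups is general, and read literally it would also require an enrolment rate by arm, which has no meaning before allocation. That weakens it as a contradiction. Retention, however, is observed after allocation and can be given by arm, and section 10.1 already covers completer counts by arm.
- The Précis, section 5.3 and the schedule of events all treat HCVR testing as screening, so the text leans towards that meaning of screened. Section 7.3.1 still uses the word for the earlier history and questionnaire step, so the denominator needs stating.

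**Conclusion.** The concern holds. The stated rule for a primary endpoint gives a percentage that is not retention, and no section calls for the percentage that is. On about 100 tested and 40 randomised, full retention reads 40%; under assumed dropout of 10% and 20% it reads 36% and 32%. If screened also includes patients excluded before HCVR testing, every figure is lower, by an amount the documents do not allow one to calculate.

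The structural point does not depend on the assumed dropout. The fault should be fixed but is not fatal: the counts will be collected, and overall retention can be recovered cumulatively if enrolled means randomised.

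**What to change.** In section 10.4.2:

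- Define retention as completers divided by participants randomised, cumulatively or by randomisation cohort, overall and by arm, with exact confidence intervals.
- Keep completers divided by screened as a separate overall measure, labelled screening-to-completion yield.
- State whether screened means screened by history and questionnaire or HCVR-tested.

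Use one label for the endpoint in the Protocol Summary and sections 4.2.1 and 10.4.2, and carry it into sections 4.1, 5.5 and 10.4.5. It would also help to tie completion to a named visit or contact, because the numerator is per-protocol completion and no section says which assessment ends the study for this purpose.

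The cost is wording only, since the counts of enrolled and completed participants are already planned. The one drawback is imprecision by arm, as the 18/20 interval shows. The overall estimate should therefore lead, with the by-arm figures shown descriptively.

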10.4.3 ANALYSIS OF THE SECONDARY ENDPOINT(S)

Observations with missing data are dropped from those analyses involving data variable.

Change in mood score using PHQ-9 score

This will be analyzed as the difference in PHQ-9 scores from baseline to final measurement between drug and placebo. The mean and standard deviation estimates of the differences will be provided.

Change in minute ventilation during HCVR testing:

This will be analyzed as the difference in minute ventilation during HCVR testing from baseline to final measurement between drug and placebo. The mean and standard deviation estimates of the differences will be provided.

Change in slope of HCVR

This will be analyzed as the difference in slope of HCVR between drug and placebo. Using a linear mixed model, we will include a predictor that is the interaction between HCVR slope and the treatment group. The mean and standard deviation estimates of the differences will be provided.

Difference in duration of abnormal breathing during periotal period:

Mean duration of abnormal breathing during perictal periods between drug and placebo will be compared. The mean and standard deviation estimates of the differences will be provided.

Difference in oxygen saturation during periotal period

Mean drop in oxygen saturation during perictal period between drug and placebo will be compared. The mean and standard deviation estimates of the differences will be provided.

Difference in CO₂ level in periotal period

Mean change in CO₂ level in periocal period compared to pre seizure baseline will be compared between drug and placebo. The mean and standard deviation estimates of the differences will be provided.

All the secondary outcome measures will be estimated using generalized linear mixed models (GLMMs), specifying an identity link for normally distributed data and the log link for right-skewed data.

Since we are interested in obtaining estimates for future studies, we will not run non-parametric analyses, which only provide p-values.

Version 01.2 Protocol:201607761 Version 20.2 Version 01.2

Assessment of adverse events

All the adverse events will be recorded. Frequency of each adverse events will be compared between the two groups and tested using one tail t-test with type I error at 0.025

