4.2.3 EXPLORATORY ENDPOINTS

Change in VRTCO₂ Change in time to VRTCO₂ Change in time to end of HCVR testing

Version 01.2 Protocol:201607761 Version 20.2 Version 01.2

We will compare all the secondary outcome and exploratory measures using generalized linear models (GLMs), specifying an identity link for normally distributed data and the log link for right-skewed data.

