7 STUDY PROCEDURES AND SCHEDULE

7.1 STUDY PROCEDURES/EVALUATIONS

7.1.1 STUDY SPECIFIC PROCEDURES

- Review medical history using electronic medical record, interviewing the potential subjects and use Iowa SSRI screening questionnaire.
- Medication history will be reviewed by direct interview with the subjects
- Screening for pregnancy will be done using questionnaire and urinary pregnancy test as applicable
- HCVR testing will be performed (as applicable) for baseline assessment prior to randomization and a follow up HCVR testing after randomized to an intervention arm.
- Eligible subjects will answer Iowa SSRI study questionnaire, and PHQ-9 scale
- Assessment of study drug adherence will be done by follow up phone calls and direct pill count at follow up visit
- Continuous comprehensive respiratory monitoring (respiratory inductance plethysmography abdominal and chest belts, nasal pressure, oro-nasal thermistry, pulse oximetry and transcutaneous carbon dioxide) will be done when the subjects are in EMU.

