10.4.11 EXPLORATORY ANALYSES

Change in VRTCO₂

Mean change VRTCO₂ between drug and placebo will be compared. The mean and standard deviation estimates of the differences will be provided.

Change in time to VRTCO₂

Mean change in time to VRTCO₂ between drug and placebo will be compared. The mean and standard deviation estimates of the differences will be provided.

Change in time to end of HCVR testing

Mean change in time to end of HCVR testing will be compared between drug and placebo. The mean and standard deviation estimates of the differences will be provided.

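### PHQ-9, minute ventilation and the exploratory HCVR measures are specified as change scores with no baseline term named; adjusting for the baseline already collected would usually give a more precise drug-placebo estimate

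*Combined protocol and SAP*

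**What the plan says.** Five endpoints are defined as change from baseline, drug against placebo.

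- PHQ-9 (10.4.3): "This will be analyzed as the difference in PHQ-9 scores from baseline to final measurement between drug and placebo".
- Minute ventilation (10.4.3): "This will be analyzed as the difference in minute ventilation during HCVR testing from baseline to final measurement between drug and placebo".
- VRTCO2 and time to VRTCO2 (10.4.11): the mean change "between drug and placebo will be compared. The mean and standard deviation estimates of the differences will be provided".
- Time to end of test (10.4.11): "Mean change in time to end of HCVR testing will be compared between drug and placebo".

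Two sentences name a model. Section 4.2.3: "We will compare all the secondary outcome and exploratory measures using generalized linear models (GLMs"). Section 10.4.3: "All the secondary outcome measures will be estimated using generalized linear mixed models (GLMMs"). Each goes on to give an identity link for normal data and a log link for right-skewed data. Neither lists fixed effects, random effects or covariates.

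The baselines exist. Section 7.1.1: "HCVR testing will be performed (as applicable) for baseline assessment prior to randomization". PHQ-9 is taken at enrollment (7.3.2), and both PHQ-9 and HCVR are repeated at the week 4 visit (7.3.3). The table in 7.3.7 marks HCVR at screening only; I rely on 7.3.3 and 4.1 for the repeat test.

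The aim is given in 10.1: "This study is designed as a pilot to obtain estimates to be used in future studies". Section 10.4.1 rules out inferential tests, and 10.5 gives no sample size calculation. The HCVR slope has its own model sentence in 10.4.3 and is not part of this point.

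**The concern.** Subtracting the baseline gives it a coefficient of exactly 1. The coefficient that minimizes variance is the regression slope of follow-up on baseline, which is below 1 when the two SDs are similar and the correlation is imperfect. A change score then over-corrects: the arm that happens to start higher tends to show the larger fall.

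A pilot whose product is a set of estimates has reason to care about this. The drug-placebo difference may be noisier than the data allow. The planned outputs, the mean and SD of change, also omit two quantities that the designer of a baseline-adjusted trial would want: the residual SD and the baseline/follow-up correlation. Section 10.4.6 tests the arms for baseline differences, but the plan does not say what follows if one is found.

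**Working it through.** **Inputs.** The plan states no SD, effect size, power or correlation for these endpoints, so it has no figure to reproduce. I assume a common SD s at both visits and a correlation ρ between 0.3 and 0.9.

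The number analysed is not settled. Section 10.6.1 gives 20 subjects in each of two locations, so 40 in all. Section 5.3 gives 20 completers per group. Section 4.1 describes two parts, each running until 20 subjects complete, with the HCVR comparison under the first. I show N = 40 (20 per arm) and N = 20 (10 per arm, if only one part contributes).

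**Step 1: one family of estimators.** Take the arm difference in follow-up minus b times the arm difference in baseline. Randomization makes the expected baseline difference zero, so any fixed b gives an unbiased contrast. With n per arm,

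variance = (2s²/n)(1 − 2bρ + b²).

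- Change score, b = 1: the bracket is 2(1 − ρ).
- Baseline-adjusted (ANCOVA), b = ρ: the bracket is 1 − ρ².
- Ratio, adjusted to change: (1 + ρ)/2.

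**Step 2: cost of estimating b.** This multiplies the adjusted variance by 1 + 1/(N − 4), which is 37/36 = 1.028 at N = 40 and 17/16 = 1.0625 at N = 20.

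| ρ | (1+ρ)/2 | N = 40 | N = 20 |
|---|---|---|---|
| 0.3 | 0.65 | 0.67 | 0.69 |
| 0.5 | 0.75 | 0.77 | 0.80 |
| 0.7 | 0.85 | 0.87 | 0.90 |
| 0.9 | 0.95 | 0.98 | 1.01 |

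Simulation under bivariate normality, 20,000 trials per case, gave 0.669, 0.770, 0.871 and 0.980 at N = 40, and 0.687, 0.799, 0.915 and 1.011 at N = 20. The standard error at N = 40 falls by about 18%, 12%, 7% and 1%.

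**Step 3: where the gain ends.** Setting the ratio to 1 gives ρ = 2/(1 + 1/(N − 4)) − 1, which is 0.946 at N = 40 and 0.882 at N = 20.

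**Step 4: unequal SDs.** With follow-up SD equal to k times baseline SD, the large-sample ratio is k²(1 − ρ²)/(k² + 1 − 2kρ). For k from 0.8 to 1.25 and ρ from 0.3 to 0.9 it runs from 0.50 to 1.00. It reaches 1 where kρ = 1, since the regression slope is then 1.

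**Step 5: chance imbalance.** The standard error of the baseline difference is √(2/20) = 0.316 SD at 20 per arm, so an imbalance above 0.5 SD in either direction has probability 0.114. At 10 per arm it is √(2/10) = 0.447 SD and the probability is about 0.26. Given an imbalance d, the change-score contrast shifts by (1 − ρ)d in size. At ρ = 0.5 and d = 0.5 SD that is 0.25 SD.

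**Step 6: the SD passed on.** The SD of change is s√(2(1 − ρ)) and the residual SD is s√(1 − ρ²). Their ratio, √(2/(1 + ρ)), is 1.24, 1.15 and 1.08 at ρ = 0.3, 0.5 and 0.7. The two are estimated about equally well: simulated coefficients of variation are about 11.5% and 11.7% at N = 40, and 17% and 17.3% at N = 20.

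For illustration, assume an effect of 0.5 s, 80% power and two-sided 0.05. The size per arm for a change-score trial against an adjusted trial is 88 and 58 (ρ = 0.3), 63 and 48 (0.5), 38 and 33 (0.7), and 13 and 12 (0.9).

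**The case against.** The strongest reply is that the plan may intend to adjust. It promises a GLMM for every secondary outcome. One change value per subject offers no within-subject repetition for a mixed model, and a log link does not suit changes that can be zero or negative. Both hint at a model for the baseline and follow-up values themselves. This stands in part: the absence of a baseline term is silence, not a refusal. But such a mixed model with free baseline means reproduces the change contrast, and only a constrained common baseline brings it close to ANCOVA. The plan says neither, and 4.2.3 and 10.4.3 name different model classes.

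Second, these are descriptive secondary and exploratory measures in a feasibility pilot, and the mean and SD of change are legitimate summaries of centrality and spread. That stands, and it limits the severity.

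Third, the gain rests on a correlation that nobody has supplied and could be negligible. That also stands, which is a reason to report the correlation.

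Two stronger readings are tempting, and the documents support neither.

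- A reader might infer that the change-score contrast is biased. Over randomization it is not. The entry limit on HCVR slope makes regression toward the mean likely in within-arm changes of that slope and of related measures, but it does not bias the comparison between randomized arms.
- A reader might infer that the pilot's SD is imprecise, or that it must oversize the next trial. It is a larger quantity, not a worse-estimated one. It is the right SD if the next trial analyses change, and the documents do not say how that trial will be analysed.

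**Conclusion.** The point holds as a low-severity gain in precision. The five endpoints are specified as change scores, no baseline term is named in either model sentence, and the needed values are already collected. Over the correlations shown, adjustment lowers the variance of the drug-placebo estimate by about 33% to 2% with 40 subjects. With 20 subjects it runs from a 31% reduction to a 1% increase. There is no gain above a correlation of about 0.95 or 0.88 respectively. The SD of change would oversize a future trial only if that trial adjusts for baseline.

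The figures assume equal SDs, the identity link, a common baseline slope in both arms, and an analysed set that still reflects the randomization. The per-protocol set (10.3) and the dropping of missing observations (10.4.3) could disturb that last condition for either method. Nothing here touches the recruitment and retention endpoints.

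**What to change.** In 10.4.3 (PHQ-9, minute ventilation) and 10.4.11 (VRTCO2, time to VRTCO2, time to end of test), state that the drug-placebo comparison is estimated from a GLM with the follow-up value as response and with arm and that endpoint's own baseline value as predictors. Use the identity link, or the log link on the follow-up value when it is right-skewed, and name the distribution. Under the log link the arm effect is a ratio of means and should be labelled so. Let this replace the unspecified GLMM for these single-follow-up endpoints, and align 4.2.3 with it.

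For each endpoint report the adjusted difference, the residual SD, the baseline and follow-up SDs, and the baseline/follow-up correlation. Keep the planned means and SDs of change as descriptive rows. State whether both locations are pooled, so that the number behind each estimate is known.

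The cost is about one sentence in each of the two analysis sections, a matching edit in 4.2.3, and one degree of freedom per model. No new data are required.

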2.3.1 KNOWN POTENTIAL RISKS

Fluoxetine is a FDA approved antidepressant medicine which is used very frequently and safely. Some patients may experience some side effects that include: Nausea, diarrhea, anorexia, dry mouth, dyspepsia, insomnia, anxiety, nervousness, somnolence, tremor, decreased libido, abnormal dreams, headache, asthenia, flu like syndrome, fever, weight loss, Flatulence, constipation, rash, pruritus, abnormal vision etc. However, rare and serious side effects are also possible which include; worsening depression, increase suicidal thoughts or actions, mood swings, acting aggressive or violent, serotonin syndrome, severe allergic reaction- trouble breathing, swelling of face, tongue, eyes or mouth, rash, hives, abnormal bleeding if you are taking blood thinner coumadin warfarin (Coumadin®), a non-steroidal anti-inflammatory drugs (NSAIDs, like Ibuprofen or naproxen), or aspirin, increase in seizure frequency and possible irregular heart rhythm called Torsades de pointes due prolonged OT.

Fluoxetine is classified by FDA as category "C" for use in pregnancy which means there is a known risk of birth defect animal fetus but there are no adequate data and well-controlled studies in human. Stopping fluoxetine suddenly can cause serious symptoms including:

- Anxiety, irritability, high or low mood, feeling restless or changes in sleep habits
- Headache, sweating, nausea, dizziness
- Shaking, confusion etc

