2.3.2 KNOWN POTENTIAL BENEFITS

Improvement in mood.

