7.3.3 FOLLOW-UP

Follow up phone call at end of week 1 and 3

Record for adverse events as reported by the participants.

If suspicious for mania, will perform full Altman self-report maniac scale

Record compliance to assigned treatment as reported by the participants.

Record current medication

Follow up visit 4 weeks (+/-1 week) after randomization

Record for adverse events as reported by the participants.

Record compliance to assigned treatment as reported by the participants and by counting pill from the pill container brought by the participants.

Record PHQ-9 score

Repeat HCVR testing

Record current medication

Video EEG study with comprehensive respiratory monitoring in EMU for paticipants enrolled at neurology clinic

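### Depression that worsens on PHQ-9 without being entered as an adverse event shows only inside a mean, and participants terminated for serious worsening drop out of that mean

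*Combined protocol and SAP*

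**What the plan says.** **Endpoint and summary.** Change in PHQ-9 is a secondary endpoint (4.2.2). Section 10.4.3 defines it: "This will be analyzed as the difference in PHQ-9 scores from baseline to final measurement between drug and placebo". The output follows: "The mean and standard deviation estimates of the differences will be provided". This matches the general rule in 10.4.1 that "continuous data descriptive statistics will be presented with the mean and standard deviation". Section 10.4.10, on tabulation of individual responses, is marked not applicable.

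**Both directions of effect are named.** Section 2.3.1 warns that "rare and serious side effects are also possible which include; worsening depression, increase suicidal thoughts or actions". Section 2.3.2 gives one benefit: "Improvement in mood".

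**Measurement.** PHQ-9 is taken at enrolment (7.3.2) and at the week-4 visit (7.3.3: "Record PHQ-9 score"), not at the calls in weeks 1, 3 and 7. No other depression scale is scheduled on treatment. The Altman scale is used only if mania is suspected (7.3.3), and the schedule in 7.3.7 places the Iowa SSRI study questionnaire at enrolment only.

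**Threshold.** Section 5.2 excludes patients with "psychosis or severe depression, or PHQ-9 score > 20". No section plans a count of participants above that value during treatment.

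**Adverse-event route.** Worsening depression and increased suicidal thoughts are named in the SAE definition (8.1.2). Deterioration of a condition present at screening is recorded as an AE (8.3). Section 10.4.4 compares AE frequencies by arm and tables serious AEs and those leading to discontinuation. It does not mention PHQ-9.

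**The concern.** The protocol expects mood to improve in some participants and, rarely, to deteriorate seriously in others. One scale covers both, and its only planned summary is a mean with its SD. A mean is the right summary for an average mood effect. It does not say how many participants got worse, and for a named harm that is the number a reader needs.

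Two separate things can go wrong:

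- A rise in PHQ-9 at week 4 that nobody enters as an AE is averaged with the improvements of the others and is not reported anywhere else.
- A participant whose worsening is recognised as serious before week 4 is terminated, has no final PHQ-9, and no longer contributes to the mean.

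The study exists to supply estimates for later trials (10.1). As planned, it passes on an average mood change but no PHQ-9-based rate of deterioration, although the scores will have been collected.

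**Working it through.** The plan gives no PHQ-9 effect, SD or worsening rate, and 10.5 has no sample size calculation, so there is no stated figure to reproduce. The check is arithmetic on assumed scores, plus a trace of where each kind of worsening is reported.

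**Inputs.** n = 20 per arm, from 40 randomised 1:1 (Protocol Summary). Assumed, with no source in the documents: k = 2 participants worsen by w = 8 points and the other 18 improve by i = 2. A negative change is improvement.

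**1. One arm, all scores present.**
- Mean = (k·w − (n − k)·i)/n = (2×8 − 18×2)/20 = −20/20 = −1.0.
- Sum of squares about the mean = 2×(8 + 1)² + 18×(−2 + 1)² = 162 + 18 = 180, so SD = √(180/19) = 3.08.
- With k = 3 the mean is −0.5 (SD 3.66). With k = 4 it is 0.0 (SD 4.10).

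**2. Does the SD reveal the worseners?** No. Ten participants at +2 and ten at −4 also give mean −1.0, sum of squares 20×3² = 180 and SD 3.08, with nobody worse by more than 2 points.

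**3. How little improvement hides them?** The arm mean is favourable when i > k·w/(n − k). Here that is 16/18 = 0.89 points. For k = 1 to 3 and w = 5 to 15, the threshold runs from 5/19 = 0.26 to 45/17 = 2.65 points.

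**4. The planned quantity is drug versus placebo.** Drug −1.0 against placebo 0 gives −1.0, against placebo −1.0 gives 0, and against placebo −2.0 gives +1.0, unfavourable to drug. The arm mean reads as a benefit only if placebo improves by less than 1.0.

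**5. If the two worseners are terminated before week 4.** Drug mean = −36/18 = −2.0, a shift of −1.0 toward benefit. The between-arm difference shifts by the same amount if no such terminations occur on placebo, and by less if some do.

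**6. Where each case is reported.**
- *Recognised as an AE or SAE:* counted under 10.4.4.
- *Recognised as an SAE before week 4:* termination and no further outcome measures (5.4.2), no early termination visit (7.3.5), missing values dropped (10.4.3) and a per-protocol set (10.3) together remove the participant from the PHQ-9 mean. Section 5.4.1 words termination after an SAE as optional and 5.4.2 as definite. The two should be reconciled, because they decide how many leave.
- *Seen on the week-4 PHQ-9, not entered as an AE:* appears only in the mean. AEs are recorded from participant report (7.3.3), seriousness is the investigator's judgement (8.1.2), and no score or change is tied to an AE entry.

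**The case against.** The strongest reply is that the plan already counts this harm. Worsening depression is in the SAE definition, AEs are asked about at every call and visit (8.3), SAEs go to the independent medical examiner within 24 or 72 hours (8.4.2), and 10.4.4 reports AEs by arm. This stands. A reader might infer that serious worsening could be reported only as an average mood benefit, and the documents do not support that. Serious worsening that is recognised has its own table and, before week 4, tends to be removed from the mean rather than averaged into it.

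A second reply is that the numbers are invented, that 10% sits poorly with a harm described as rare, and that a one-arm mean is not the planned contrast. This also stands. A reader might take −1.0 as the planned result, but it is one arm with assumed inputs, and step 4 shows the sign can reverse. A PHQ-9 rise is, however, a wider event than the rare serious harm.

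A third is that a PHQ-9 above 20 during treatment is already covered, because a newly met exclusion criterion may end participation (5.4.1). That is a discretionary route for the individual. It gives no count in the results.

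Finally, mean and SD are conventional for a pilot after centrality and spread. That supports keeping the mean, but does not argue against a count beside it.

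**Conclusion.** The point holds as a reporting gap with two parts. PHQ-9 worsening at week 4 that is not entered as an AE is visible only inside a mean and SD, neither of which identifies it. Participants terminated for serious worsening before a final score leave the PHQ-9 mean, which biases that mean toward benefit. The drug-placebo contrast is biased in the drug's favour to the extent that such terminations are more frequent on drug.

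The size cannot be fixed from the documents. Under the assumed inputs, two worseners of 8 points sit inside an arm mean of −1.0 (SD 3.1), and removing them gives −2.0. These figures rest on 20 per arm, the chosen score changes and, for the second, termination before week 4. What the PHQ-9 result would show between arms depends on placebo.

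The addition is worth making because it is cheap and concerns a harm the protocol names. It does not call the mood endpoint itself into question.

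**What to change.** Keep the mean change in 10.4.3 as the mood endpoint. Add to 10.4.4 a descriptive table by arm, with all randomised participants as denominator, giving number and percentage:

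- whose PHQ-9 rose from baseline by at least an amount that the sponsor fixes in advance (5 points is only an assumed example);
- whose PHQ-9 was above 20 at follow-up (given the entry limit, each of these has risen since baseline);
- who were terminated for worsening depression or suicidal thoughts, counted as worsened whether or not a final score exists;
- who have no final PHQ-9 for any other reason, with the reason, shown separately and not counted as worsened or improved.

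These rows can overlap, so also give the number of participants who worsened by any of the first three, each counted once. List baseline and week-4 scores by arm beside the depression-related AEs and SAEs, and amend 10.4.10 to refer to that listing. No test is needed.

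The cost is SAP wording, one small table and one listing from data already collected. No visit, dose or clinical rule changes.
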